Study duration	16 months (four months preintervention period and 4-month interval between each step (three steps))
Sample size and power calculation	The sample size of six hospitals was estimated assuming 30% antimicrobial prescription adherence with the paper-based prescribing guidelines (reference), and assuming 0.05 intra-cluster correlation coefficient. This will have 80% power to be able to detect a 15% minimum difference in adherence after introduction of the mobile phone app prescribing guidelines (intervention) at a 0.05 significance level.
Randomization and blinding	Simple random sampling will be used to select the order (step) of interventions implementation for a group of hospitals (two hospitals per group and one group per step). Neither hospitals nor investigators will be blinded to the timing of intervention.
Intervention	A MicroGuide antimicrobial prescribing guideline mobile phone application and

	AMS training
Reference	Paper-based antimicrobial prescribing guidelines
Outcomes/Primary endpoint	The proportion of antimicrobial prescriptions adherent with prescribing guidelines delivered by mobile phone app versus paper-based prescribing guidelines at month 16 (12 months' exposure in each group)
Secondary endpoints	
 1. Total antimicrobial defined daily doses (DDDs) prescribed in mobile phone app versus paper-based groups after 12 months' exposure in each group 2. Proportion of patients prescribed antimicrobials by the oral route in mobile phone app versus paper-based groups after 12 months' exposure in each group 3. AMS knowledge level of prescribers prescribed in mobile phone app versus paper-based groups after 12 months' exposure in each group 4. Prescriber satisfaction/acceptability of the prescribing guidelines in mobile phone app versus paper-based groups after 4 months' exposure in each group 5. Total costs of antimicrobials prescribed in mobile phone app versus paper-based groups after 12 months' exposure in each group 6. Proportion of patients admitted to hospital receiving an antimicrobial prescription before and after introduction of the paper-based prescribing guidelines; and the mobile phone app prescribing guidelines + AMS training after 12 months' exposure in each group
Outcome measurement	
 • Point prevalence surveys (PPS) of hospital antimicrobial use • Prescriber questionnaires • AMS knowledge surveys of prescribers

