3.4 Randomization and blinding

Six participating hospitals have been divided into 3 pairs based on the geographical location and convenience for conducting the surveys. The first paired hospitals include two provincial hospitals from the north of Laos (Luang Namtha and Xiengkhuang), the second pair includes hospitals in the center (Mahosot Hospital-central referral hospital and Vientiane provincial hospital which is 80 km from the center of the capital to the north). The third pair includes two provincial hospitals from the south of Laos (Savannakhet and Salavan).

As there are only 3 orders to be assigned, clusters will be randomly assigned to one of three start dates using a simple random sampling, to have access to the study intervention. Three paired hospitals (LNT+XK, MS+VTP and SVK+SV) will be written on three different paper slips (similar paper size and paper texture). All slips will be folded to the same size and put in the non-transparent container, covered firmly and mixed well. A person who is not related to the study will be asked to pick up the paper slip one by one and read out to the PI and a co-investigator. Simple random sampling processes will be performed before the start of the project and the order of each paired hospital to intervention introduction will be recorded. At month 4 after the start of the project, the intervention will be introduced to the first selected paired hospital, then every four months each pair of hospitals will be rolled out from the reference phase to the intervention phase until all have started the intervention. This will give 1:1 ratio of intervention vs reference period of observation (figure 2). We will therefore be able to compare the effects of the reference and intervention over a reasonable period of time. Neither hospitals nor investigators will be blinded to the introduction of the intervention.

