3.5 Study intervention and reference

Before starting the project, PI, co-investigators and research team will visit each participating hospital to discuss about the project's objectives and how we would like to conduct this project during 16 months to the directors of the hospitals. These six hospitals have already participated in Global PPS, led by the PI and research team of this project. Hospital staff will be informed about the study by the PI and a director of hospital (also co-investigator) before starting the project and all prescribers in participating hospitals will be encouraged to participate in the training and surveys.

a. Pre-study phase

Four participating hospitals (MS, XK, LNT and SV) in this study have already participated in Global-PPS since 2017, whilst VTP participated in 2018 and SVK in 2019. Antimicrobial prescription data of all six hospitals are available for the whole of 2019. This is the period when there were no available Lao therapeutic and prophylactic antimicrobial prescribing guidelines. These data will be used in this project to compare the change in proportion of antimicrobial prescriptions and the change in administration route before and after the introduction of the prescribing guidelines (both paper-based and mobile phone app versions). To be able to answer our study question, Lao therapeutic and prophylactic antimicrobial prescribing guidelines were developed to be introduced at month 0 of the project. Details of Lao therapeutic and prophylactic antimicrobial prescribing guidelines are described below.

Lao antimicrobial prescribing guidelines

Lao National antimicrobial prescribing guidelines are based on existing Lao treatment guidelines, current data on infectious disease pathogens and antimicrobial susceptibility patterns in Laos and international antimicrobial prescribing/treatment guidelines (e.g. WHO, CDC, NICE, ISID, Sanford). The guidelines are separated into paediatric and adult guidelines for ease of use. These guidelines include recommendation for therapy, prevention and antibiotic stewardship.

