After the first paired hospital is randomly selected to have access to the mobile phone app prescribing guidelines at month 4, the second pair of hospitals will be randomly selected to have access to the mobile phone app at month 8, and the last pair of hospitals will have access to a mobile phone app at month 12 (Figure 2).

The order of activities at the start of the project are listed below (these activities will be applied to all six hospitals, one by one):

1. PPS on hospital antimicrobial use for all 6 hospitals (Appendix A1, A2 and A3)
2. AMS knowledge survey (Appendix A5)
3. Pre-prescribing guidelines survey (Appendix A9)
4. Access to paper prescribing guidelines for all 6 hospitals
5. Introductory session to paper prescribing guidelines (Appendix A6)
6. PPS reports (Appendix A4)

Activities in the reference phase after the start of the project (month 0) until the last paired hospital is assigned to the intervention (month 12) are listed below:

1. PPS on hospital antimicrobial use (Appendix A1, A2 and A3)
2. PPS reports (Appendix A4)

c. Intervention phase

c.1 Antimicrobial Prescribing guidelines mobile phone application (MicroGuide)

Both paediatric and adult antimicrobial prescribing guidelines will be transferred to [MicroGuide](#); which is a medical guideline application. MicroGuide was launched in 2013 and has been adopted by 114 medical organizations, with more than 100,000 users in 173 countries. MicroGuide is an offline application, free-of-charge for the individual users. The app can monitor the number of users and which guidelines are being accessed.

The app will be installed to the personal smart phones of local physicians by the PI. The project will not provide a smart phone to any physician without one (approximately <10% of physicians in provincial hospitals– unpublished data). The contents of the mobile app guidelines will be the same as the paper version but using hyperlinks to information, rather than displaying it as in paper guidelines. Both mobile app and paper guidelines will be available in Lao and English languages.

c.2 Antimicrobial stewardship (AMS) training

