Training date, time and venue: the session will take maximum 4±1 hours in total (including installation and registration step by step, also include discussion/questions). Training date, time and venue will be informed to all doctors one week in advance and again 3 days before starting the session. The session will be run in each hospital separately (2 hospitals on month 4, another 2 on month 8 and the last 2 hospitals on month 12) after conducting point prevalence survey (PPS) of hospital antimicrobial use. Verbal consent will be asked from participants to record each participant's name, age, sex, working position, department, years of work and phone number onto the session registration sheet.

Instructor: the principal investigator of the study will be the training instructor. Training will be given in the format of PowerPoint presentation and showing the real process of each step, followed by questions and discussion.

Training material: A handout of the training will be provided to all participants (the same standard session for all hospitals).

Training details: training session will include introduction to the MicroGuide, how to register, how to install, how to use step by step and how to update the App.

A8. Introductory (paper/App guidelines) session registration sheet

Introductory session of the use of therapeutic and prophylactic antimicrobial prescribing guidelines

Date: _____, Time: _____

Venue: _____, Hospital: _____

Participants list:

No.	Name and Surname	Age	Sex	position	Department	Year of graduation from medical school	Phone number
1							
2							
3							
4							
5							
6							
7							
8							
9							
10							
11							
12							
13							
14							
15							
16							
17							
18							
19							
20							
21							
22							
23							
24							
25							
26							
27							
28							
29							
30							

A9. Pre-prescribing guideline Survey

Pre-prescribing guideline Survey

Date: ___/___/____, Year of graduation from medical school: _____, Speciality: _____,
Department: _____ Hospital: _____

1. How frequently do you prescribe antimicrobial (s)?

Daily Nearly every day Weekly Monthly Never

2. How often do you access any antimicrobial prescribing guidelines?

Daily Nearly every day Weekly Monthly Never

3. Do you have a smart phone? Yes No Sometimes; If answer is "No", you do not have to answer question 4, 5 and 6

4. Do you carry your smart phone with you at work? Yes No

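### The full crossover order is drawn before month 0 and read out to the PI, so the paper comparator is introduced with every crossover date known to its instructor; a later draw released pair by pair would cheaply reduce this

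*Combined protocol and SAP*

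**What the plan says.** Section 3.4 (Randomization and blinding) puts the three hospital pairs on three paper slips. Someone unconnected with the study is to "pick up the paper slip one by one and read out to the PI and a co-investigator". On timing it says: "Simple random sampling processes will be performed before the start of the project". The full sequence of pairs is written down at that point. The calendar is fixed: "At month 4 after the start of the project, the intervention will be introduced to the first selected paired hospital", and the other pairs follow at four-month intervals. Knowing the order is therefore knowing every date.

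The Trial synopsis adds: "Neither hospitals nor investigators will be blinded to the timing of intervention". Section 3.4 says the same about the introduction of the intervention.

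Four other places bear on who could act on this knowledge:

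- Section 3.5, opening paragraph: the PI and a hospital director, described as also a co-investigator, tell staff about the study before it starts.
- Section 3.5 b: the PI's contact details are in the guidelines for questions. The same subsection says "the second pair of hospitals will be randomly selected to have access to the mobile phone app at month 8".
- Appendix A6: the PI is the instructor for the month-0 paper session, which is the same standard session in every hospital.
- Appendices A7 and A12, on the app and stewardship sessions: "Training date, time and venue will be informed to all doctors one week in advance", with a reminder three days before.

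The documents do not say that the order is concealed, or that it is released step by step.

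**The concern.** Paper-phase adherence is the comparator for the primary endpoint. The Introduction expects apps to be more attractive to physicians than bulky handbooks. A hospital that knows the app is four months away has less reason to adopt the paper guideline than one facing twelve months. An instructor who knows the order could, without intending it, give the paper introduction less weight where it will soon be supplemented.

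Either effect would lower paper adherence according to each pair's assigned date. Hospital effects do not absorb that, because it changes within a hospital over time. Survey-month effects do not absorb it either, because it differs between pairs in the same month. The likely direction favours the app.

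The early draw serves no purpose during the first four months: all six hospitals have the same activities until the month-4 survey is done.

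**Working it through.** **The plan's own figure.** The only design figure is 80% power for a 15-point difference from 30%, with six hospitals and an intra-cluster correlation of 0.05 (section 3.3). The number of prescriptions per hospital per survey is not given, so the figure cannot be reproduced. A Hussey-Hughes calculation reaches 80% two-sided at about 36 to 45 prescriptions per hospital per survey. The present point does not depend on it.

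**Who knows the order, and when.** Early knowledge is documented for the PI and one co-investigator (3.4). For hospitals it is permitted (synopsis) but not described. For prescribers the only stated notice is one week before the app session (A7, A12).

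**Size if paper adherence dips before crossover.** The documents give no size, so the dip d, in percentage points, is an assumption. The plan specifies a logistic mixed model; a linear least-squares model is used here as an approximation.

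Inputs: three pairs crossing at months 4, 8 and 12, with the entry-month survey taken before the app is given (3.5 c.3). The app indicator x is therefore 1 only at surveys after months 4, 8 and 12 respectively. The outcome is zero except for −d at each pair's last paper survey, so the fitted app coefficient is the bias:

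bias = Σ(r × outcome) / Σr², where r is x after removing the fitted effects. Both hospitals in a pair behave alike, so one row per pair is enough.

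*Hospital and survey-month effects:* r = x − pair mean − month mean + grand mean.

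- Months 4–16: pair means 3/4, 1/2, 1/4; month means 0, 1/3, 2/3, 1; grand mean 1/2. At the last paper surveys r = −0.250, −0.333, −0.417, sum −1.000. Σr² = 6 − 4(0.875) − 3(14/9) + 12(0.25) = 0.833. Bias = 1.000d/0.833 = **1.20d**.
- Months 0–16: pair means 0.6, 0.4, 0.2; month means 0, 0, 1/3, 2/3, 1; grand mean 0.4. r = −0.200, −0.333, −0.467, sum −1.000. Σr² = 6 − 5(0.56) − 3(14/9) + 15(0.16) = 0.933. Bias = 1.000d/0.933 = **1.07d**.

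*Hospital effects only:* r = x − pair mean.

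- Months 4–16: (0.75 + 0.50 + 0.25)d / (0.75 + 1.00 + 0.75) = 1.5d/2.5 = **0.60d**.
- Months 0–16: (0.6 + 0.4 + 0.2)d / (1.2 + 1.2 + 0.8) = 1.2d/3.2 = **0.38d**.

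| Assumed d | Hospital + survey month | Hospital only |
|---|---|---|
| 2 points | 2.1–2.4 | 0.8–1.2 |
| 5 points | 5.4–6.0 | 1.9–3.0 |
| 10 points | 10.7–12.0 | 3.8–6.0 |

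The target difference is 15 points. The Statistical analysis section names clustering by hospital and an exposure-duration interaction. It does not name survey-month effects, so both sets of figures are shown.

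**What staged release would leave** (hospital and survey-month model). The last pair is identified once the second is released. A dip in that pair's last paper survey alone gives 0.417d/0.833 = 0.50d (months 4–16) and 0.467d/0.933 = 0.50d (months 0–16).

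Alternatively, let the dip in every waiting pair scale with its chance of being next: 1/3 before month 4, 1/2 before month 8, 1 before month 12. Month 4 then contributes nothing, because all pairs dip equally. For months 4–16, month 8 contributes 0.417 × 1/2 and month 12 contributes 0.417, giving 0.625d/0.833 = 0.75d. For months 0–16 the sum is 0.467 × 1.5 = 0.700, giving 0.700d/0.933 = 0.75d.

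The share of the assumed bias removed thus runs from 1 − 0.75/1.07 = 30% to 1 − 0.50/1.20 = 58%.

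**The case against.** The case against a serious problem is substantial, and most of it stands.

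- **Prescribers are not shown to know their date.** A reader might infer that the paper guideline is used throughout with each crossover date known. The documents support this only for the PI and one co-investigator. Section 3.5 describes telling staff about the study, not the order, and does not say that a hospital director attends the draw. Not being blinded to timing describes an open trial; it is not a plan to announce dates.
- **The app does not replace paper.** A reader might infer that a hospital near crossover is about to lose the paper guideline. The note to 3.5 c.3 says prescribers keep it, and 3.5 c.1 says the contents are the same. This weakens the motive to postpone uptake.
- **Delivery is standardised.** The paper session is short, has a handout and is the same everywhere (A6). The team stays out of individual prescribing decisions (3.5 b). Nothing suggests that delivery would vary by pair.
- **Section 3.5 b need not contradict 3.4.** The phrase about month 8 can be read as attaching the month to access, consistent with a single earlier draw. It needs tidying and is not evidence of two procedures.
- **The direction is not certain.** If pairs with longer to wait used paper less at their earlier surveys, the model with survey-month effects would give a small bias the other way, −0.07d to −0.20d.
- **Early knowledge has planning value.** One team travels to each cluster in turn (3.1) and the PI installs the app on personal phones (3.5 c.1).

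What remains is that standardising the session's content does not protect later uptake, and that the one-week notice announces a session without concealing the date beforehand.

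**Conclusion.** The point holds as a cheap improvement, at the priority of something to consider. The PI introduces the comparator knowing every crossover date, hospitals may learn theirs, and the design does not need this before month 4. The documents do not show that the comparator will be weakened, and they give no basis for a particular size.

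Conditional on an assumed dip of d points in each pair's last paper survey, the upward bias is about 1.1d to 1.2d with hospital and survey-month effects, or 0.4d to 0.6d with hospital effects only. These figures rest on a linear approximation, on the entry-month survey preceding the app, and on equal dips in all pairs. Hospitals and pairs were fixed before the draw and the surveys take all eligible charts or prescriptions, so the risk lies in how paper is delivered and used, not in which hospitals or patients are included.

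**What to change.** Keep the slips and the independent drawer; change when the draw happens and who hears the result.

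1. In 3.4, hold the draw after the month-0 survey of antimicrobial use, the baseline prescriber surveys and the paper introductory sessions are complete in all six hospitals, and before month 4.
2. Have the independent person keep the recorded order sealed and release only the next pair to the PI, when travel planning for that step requires it. Tell that pair's hospitals at the one-week session notice already in A7 and A12.
3. Align the synopsis with this by saying that hospitals learn their date at that notice. In 3.5 b, refer to the single recorded draw.

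The cost is protocol wording and shorter lead time for the team and the hospital directors; visits and surveys do not change. The gain is partial: every hospital knows the app is coming, and the last pair is known by elimination once the second is released.

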3.1 Study design

The study design will be an open cohort stepped wedge cluster randomized controlled trial (SW-CRT) in six central/provincial hospitals across Laos. SW-CRT is appropriate in the Lao context because it requires fewer sites than a parallel cluster trial, but has similar observational periods for reference and intervention phases. As the interventions will be delivered by one team travelling to each cluster in turn, implementing in stages will be more practical. In addition, all participating hospitals will have access to the novel interventions at the end of the study. Prescribers are allowed to move in and out of clusters during the trial.

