1. Mahosot Hospital - 16 wards, including infectious disease paediatrics, general paediatrics, neonatal-paediatric intensive care unit (ICU), ICU adult, general medicine, gastro-intestinal, cardiovascular, infectious disease adult, lung, psychology, ear-nose-throat (ENT), abdominal surgery, uro-surgery, plastic surgery, general surgery, post operation room, obstetrics and gynaecology (OBGY)
2. LNT provincial hospital - 7 wards, including medicine, surgery, paediatrics, OBGY, intensive care unit, ENT
3. XK provincial hospital - 11 wards, including cardiology, infectious disease, OBGY, ICU adult, ICU paediatrics, surgery, post operation, medicine, eyes, and specialty ward (mixture of medicine, surgery, OBGY or paediatric patients – this ward is for patients who need private and more comfortable room)
4. VTP provincial hospital - 5 wards, including paediatrics, OBGY, medicine, surgery and ICU
5. SVK provincial hospital - 9 wards, including medicine 1, medicine 2, lung, infectious diseases (HIV/AIDs ward), surgery, OBGY, ICU and specialty ward
6. SV provincial hospital - 7 wards, including medicine 1 (general medicine), medicine 2 (mostly infectious disease patients), lung, paediatrics, surgery, OBGY and ICU

Survey dates and times – PPS will be conducted every four months throughout the year. There will be 5 PPS in total from the start of the project (month 0) until the finish date of the project (month 16) (Figure 2).

PPS must be completed within a maximum of 5 consecutive working days from the start date of collecting data in hospital of that PPS round. All hospital charts of all admitted patients on a ward must be screened at 8 o'clock in the morning on the day of the survey. Survey days will be from Monday to Friday, excluding public holidays.

Survey staff

- Research staff, *OR*

- Local doctor who is familiar with their own local hospital charts and has been trained on data collection for this project

Inclusion and exclusion criteria

Inclusion criteria

1. All patient hospital charts from all in-patient wards at 8:00 o'clock in the morning of a survey day will be counted as the denominator
2. All patient hospital charts from all in-patient wards with any kind of antimicrobial agent (s) prescribed at 8 o'clock in the morning of a survey day will be counted as numerator.

Definition for IPD surveys

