All data will be entered by PI and trained research staff. All complete survey forms will be kept securely in a locked filing cabinet. Only the PI of the project and project data management team will have access to the raw data. All electronic data will be kept securely, protected by password access with automatic daily backup on the server at Lao-Oxford-Mahosot Hospital-Wellcome Trust Research Unit (LOMWRU) office and regular offsite tape backups. All scanned OPD prescription sheets will be appropriately destroyed within one month after the scanned date. Anonymized data from PPS will be fed back to the participating hospitals and Ministry of Health through a project-generated computer dashboard and reports one month after each PPS in each hospital. Data checking and cleaning will be done by the PI after each survey. Data inconsistency will be discussed with the research team immediately.

Statistical analysis

Normally distributed continuous baseline characteristics will be summarized with means and standard deviations. Skewed continuous data will be summarized using median and inter-quartile range. Categorical data will be presented as frequency and percentages. A logistic mixed effects regression model will be used to compare the proportion of antimicrobial prescriptions adherence

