Yes No Sometimes

7. How often do you access the provided mobile phone app prescribing guideline?

Daily Nearly every day Weekly Monthly Never

8. How often do you access other prescribing guidelines?

Daily Nearly every day Weekly Monthly Never

9. How would you rate this app overall?

- Very good and I will continue to use it Good but needs a bit more editing and I will continue to use it
 Good but I prefer paper-based version moderate but I prefer paper-based version
 Not good and I prefer paper-based version Others _____

Please give comments to improve this app:

A12. Antimicrobial stewardship (AMS) training

Training objective: to raise awareness of antibiotic good prescribing practices

Trainees: this session will be given to all hospital doctors in all study hospitals at the start of the intervention period of each paired hospital (month 4, month 8 and month 12).

Training date, time and venue: the session will take a maximum of 30 minutes with 10 minutes of discussion/questions. Training date, time and venue will be informed to all doctors one week in advance and again 3 days before starting the session. The session will be run in each hospital separately (2 hospitals on month 4, another 2 on month 8 and the last 2 hospitals on month 12) after conducting point prevalence survey (PPS) of hospital antimicrobial use, completing prescriber feedback survey and after finished introductory session of the prescribing guideline mobile phone App. Verbal consent will be asked from participants to record participant's names, age, sex, working positions, departments, years of work and phone number onto the session registration sheet.

Instructor: the principal investigator of the study will be the training instructor. Training will be given in the format of PowerPoint presentation, followed by question and discussion.

Training material: Handout of the training will be provided to all participants (the same standard session for all hospitals).

Training details: All training details already exist in the prescribing guidelines. The majority of training will be on the section of AMS and some part of the training will be from the therapeutic and prophylaxis sections. This training session will include good practice of antibiotic prescriptions, the idea and benefits of intravenous therapy to oral therapy switch, choice of prescription when patients report penicillin allergy.

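### The plan does not say who assigns guideline adherence, by what written rules, or whether coding is masked to study phase, although the investigators are unblinded

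*Combined protocol and SAP*

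**What the plan says.** **Blinding.** Section 3.4: "Neither hospitals nor investigators will be blinded to the introduction of the intervention". The synopsis says the same about the timing of the intervention.

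**Delivery.** Section 3.1 refers to one delivering team: "As the interventions will be delivered by one team travelling to each cluster in turn". Section 3.5 adds: "The app will be installed to the personal smart phones of local physicians by the PI". Appendices A7 and A12 name the principal investigator as instructor for the app session and the stewardship training. Appendix A6 names the same person for the paper-guideline session.

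**Data handling.** Section 3.7, under data management and monitoring, has three relevant sentences: "All data will be entered by PI and trained research staff"; "Only the PI of the project and project data management team will have access to the raw data"; and "Data checking and cleaning will be done by the PI after each survey". Surveyors are research staff or, for inpatients, a trained "Local doctor who is familiar with their own local hospital charts". The outpatient survey also allows a trained local doctor.

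**The outcome.** Section 3.6 defines three levels. Right agent and dose is full adherence, right agent with wrong dose is partial, and a different agent is non-adherence. Section 3.5 says that each disease section of the guidelines offers primary and alternative regimens, with notes on allergy and toxicity.

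**What is absent.** No section names the person who assigns the level, the time at which it is done, a coding manual, a second coder, an agreement check or any masking.

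**The concern.** Hospital and survey date together reveal the study phase of every record. Anyone who classifies a record with those fields in view knows whether it comes from an app period. If doubtful records were resolved more favourably in one phase, the error would line up with study arm. The mixed model in the statistical analysis section adjusts for clustering by hospital; it cannot separate such an error from an effect of the app.

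The primary endpoint is at stake, and the protection is cheap. The adherence definition uses neither hospital nor date, so the coder does not need them.

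**Working it through.** **1. Where the coding step sits.** The inpatient and outpatient forms (Appendices A2 and A3) record agent, unit dose, doses per day, route, diagnosis, diagnosis site and type of indication. Neither has an adherence field, so the level is apparently assigned later from the record. The report template (Appendix A4) and the dashboard description in Section 3.7 list no adherence result, so coding need not be finished after each survey.

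**2. How much is rule-based.** Once a guideline entry is chosen, comparing agent and dose is mechanical. Choosing the entry, or scoring against it, is less so in three situations:
- An alternative regimen may depend on allergy, but the forms have no allergy field.
- The forms ask whether a reason is in the notes (yes/no), so records without one are foreseen. Section 3.6 has no rule for a record that matches no entry.
- In the 2018 survey cited in the introduction, 43% of patients received more than one antimicrobial. Section 3.6 does not say how to score a combination that is only partly right.

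**3. The plan's own figure.** Section 3.3 gives 80% power for six hospitals, 30% reference adherence, a 15% difference (read as 30% v 45%), intra-cluster correlation 0.05 and significance level 0.05 (two-sided assumed). It does not give m, the number of prescriptions per hospital per survey, so 80% cannot be reproduced. It can be solved for m with the Hussey-Hughes variance:

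Var = I·s²(s² + T·t²) / [(I·U − W)s² + (U² + I·T·U − T·W − I·V)t²]

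- Four periods and three sequences of two hospitals give I = 6, T = 4, U = 12, W = 4 + 16 + 36 = 56, V = 2(9 + 4 + 1) = 28.
- Total variance at the mean proportion is 0.375 × 0.625 = 0.2344, so t² = 0.05 × 0.2344 = 0.01172.
- With m = 45, s² = 0.95 × 0.2344 / 45 = 0.00495.
- Var = 6 × 0.00495 × (0.00495 + 0.04688) / (16 × 0.00495 + 40 × 0.01172) = 0.00281. The standard error is 5.30 points and power is 81%; at m = 44 power falls just short of 80%.

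Using the reference-arm variance instead, m is 40. With the month-0 survey as a fifth period, m is 36 to 41. The stated power is therefore consistent with about 36 to 45 prescriptions per hospital per survey. At exactly 80% power the standard error is 15 / (1.960 + 0.842) = 5.35 points.

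**4. Illustration A: share needing judgement.** Bias = share needing judgement × differential favourable resolution (both assumed).
- Low: 0.10 × 0.10 = 0.01, or 1 point (1/15 = 7% of the target difference).
- High: 0.20 × 0.20 = 0.04, or 4 points (4/15 = 27%).

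**5. Illustration B: lenient coding with no true effect.** Suppose adherence is 30% in both phases and a share e of non-adherent prescriptions is coded adherent in app periods only (assumed). The spurious gain is 0.70 × e. With b = gain / 5.35, the two-sided false-positive rate is 1 − Φ(1.960 − b) + Φ(−1.960 − b).

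| e | Gain (points) | Share of 15 | False-positive rate |
|---|---|---|---|
| 0 | 0 | 0 | 5% |
| 2% | 1.4 | 9% | 5.8% |
| 5% | 3.5 | 23% | 10.0% |
| 10% | 7.0 | 47% | 25.8% |

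Larger surveys make this worse, because the standard error shrinks and the bias does not. At 100 prescriptions per hospital per survey (four periods, standard error 3.41 points) the last three rates become 6.9%, 17.6% and 53.6%.

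**The case against.** A reader might infer that the team delivering the app also codes adherence. The documents do not support that. Raw-data access goes to the principal investigator and a data management team, and nothing says that this team installs the app or trains doctors. Data entry is shared with research staff, and entry and cleaning are not the same as classification. Local doctors who survey belong to the receiving hospitals. The supportable statement is that the coder and any masking are unspecified, while the person who delivers the app has hands on the data.

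It would also go too far to call adherence purely a matter of judgement, or diagnosis a free-text field. The definition rests on agent and dose, and the forms do not show how diagnosis is entered.

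Nor is the outcome unprotected. The three levels are pre-specified, guideline content is the same in both phases, data collectors are trained, survey definitions are fixed, and staff are approached only over inconsistent counts or unclear handwriting. These features constrain coding, but none of them hides phase from the coder.

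The direction of bias is not established, since the same instructor also teaches the paper-guideline session. The error rates are assumptions, and the whole 1-to-4-point range lies below one design standard error (4 / 5.35 = 0.75). Both objections stand. They limit what can be said about size; they do not supply the missing procedure.

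**Conclusion.** The point holds as a gap in specification. The plan does not name the adherence coder, gives no rules for ambiguous records and plans no masking, while investigators are unblinded and the principal investigator both delivers the intervention and handles the data. Unmasked coding could bias the primary endpoint.

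The documents show neither that it would nor in which direction, and they give no error rate. The 1 to 4 points, and the 1.4 to 7.0 points under lenient coding, are illustrations under assumed rates. The false-positive rates further assume that leniency occurs in app periods only and that the normal approximation holds. The stated power is neither confirmed nor refuted, and masked coding would not change it. This is an inexpensive improvement that should be made.

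**What to change.** **Before the month-8 survey.** Under Section 3.5 the month-4 survey precedes app introduction, so month 8 yields the first app-phase data. By then:
1. Name the coders.
2. Lock a written rule set or look-up table from diagnosis, indication and age/weight group to the guideline agents and doses. Include rules for combinations and for records with no matching entry.
3. Assign full, partial or non-adherence by program from the ODK fields.

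**Residual records.** Existing staff code the records that still need judgement, with all rounds together and in random order. The extract should omit hospital, survey date, survey number, antimicrobial start date, ward name and surveyor. Start date can reveal the round, and some ward types in Section 3.7 are listed for only one hospital. Double-coding a sample and reporting agreement would be a useful addition.

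**Cost.** No separate assessor is needed, but building the table for adult and paediatric guidelines, programming and preparing the extract take staff time that the documents do not cost. Final coding moves to batches. Outpatient scans are destroyed within one month, so coding must rely on the ODK record, and borderline outpatient records cannot be checked against source later.

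**What remains.** Chart abstraction stays unblinded, including where local doctors do it, and staff may recognise records that they collected. Changes in how prescribers document diagnoses are also untouched. State the abstraction bias as a limitation.
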